5.4 Study variables

5.4.1 Variables result, exposure or effect

Main Outcome Variable:

Acceptability and usability of VR exercises: This will be measured using a user satisfaction questionnaire and the System Usability Scale (SUS). HE will managen after the last session (the eighth).

Secondary Outcome Variables:

Cognitive function (memory and attention), measured through standardized tests: - Specific to attention and memory (Digits, TMT [Annex 3], SDMT [Annex 4]).

- General cognitive function tests:
- Montreal Cognitive Assessment (MoCA) [anexo 5]
- Mini-Mental State Examination (MMSE) [anexo 6]

The evaluations will be carried out before starting the training program and at the end of it (after the eighth session).

Usability of the system by professionals:

This will be evaluated using the System Usability Scale (SUS) for patients and professionals [Annex 7 and 8]. It will be administered to professionals after completing the training program.

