5.3 Participating population

Source population: The source population of the study will be the patients who attend the cognitive rehabilitation program at the Centro Sociosanitario El Carme (CSSC) in Badalona Serviceis Asistencianals.

Location: El Carme Socio-Health Center (CSSC), Badalona, Spain.

Selection period: Participants will be selected from September to October 2023.

Inclusion criteria:

- Participants must be at least 60 years old, with no maximum age limit.
- Participants must be classified as having mild cognitive impairment with an MMSE score > 23.
- Participants must be currently attending cognitive rehabilitation sessions at the CSSC Day Hospital.
- Participants must be able to give informed consent or, in the event of incapacity, consent must be obtained from their legal representative.

- Exclusion criteria

- Patients with a serious or unstable illness that may interfere with their participation in the study.
- Patients with severe psychiatric disorders, such as psychotic disorders, delusions or hallucinations that may be exacerbated by the use of virtual reality.
- Patients with severe visual limitations that would prevent the use of virtual reality.
- The presence of eye diseases that cause blurred vision that cannot be corrected with contact lenses or glasses.
- Presence of hearing pathologies that cause a significant decrease in hearing without hearing aids.
- High sensitivity to motion sickness.
- Epileptic subject.
- Patients who are unable or unwilling to give informed consent.

Withdrawal criteria

Withdrawal criteria will include the appearance of health problems that may interfere with continued participation in the study, or withdrawal of consent by the participant.

Sampling type

The type of sampling will be non-probabilistic sequential. All patients who meet the inclusion criteria and do not meet any of the exclusion criteria will be invited to participate until the desired number of participants is reached.

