5.4.2 Other variables

- Age
- Sex
- Etiology of cognitive impairment
- Schooling
- Exposure to other treatments: Any additional medication or cognitive therapy that the patient is simultaneously participating in will be recorded.

5.5 Study Evaluations:

Visit	Procedures		
Selection visit (Pre-study)	Informed consent, collection of demographic data and results of cognitive function variables		
Visit 1 (Session 1)	Starting VR training sessions		
Visit 2 (Session 8 - Final)	Completion of the VR training sessions, questionnaires on cognitive function and satisfaction and usability variables.		

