6. SOURCES OF OBTAINING AND MANAGING DATA

6.1 Data source

Data collection in this pilot study will be carried out through primary sources. Data will be obtained directly from participants:

The acceptability and usability of the VR exercises will be measured through questionnaires that participants will complete after each VR session.

Cognitive function and quality of life will be measured through standardized tests that participants will complete before, during and after the VR training program.

Variables such as age, gender and degree of cognitive impairment will be collected through interviews and medical records.

Exposure to other treatments will be recorded through interviews with participants and review of their medical records.

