7. PROTECTION OF PERSONS UNDER INVESTIGATION

7.1 Benefit-risk evaluation for research subjects

This interventional study uses virtual reality (VR) for cognitive stimulation of patients with cognitive impairment. The following potential risks and benefits to participants have been identified, along with specific mitigation strategies for the identified risks.

Risks and Mitigation Strategies:

1- Side effects of VR: Some patients may experience dizziness or disorientation with VR. To mitigate this risk, static or smooth motion VR experiences will be designed, and the technology will be introduced gradually. Side effects will be carefully monitored, especially in patients with conditions that may increase risk.

2- Patient acceptance: Since VR is a relatively new technology, it can be intimidating for some patients. To overcome this barrier, the potential benefits of VR will be effectively communicated and patient concerns will be proactively managed. Engagement with healthcare personnel during the process can improve patient acceptance and adherence.

3- Technical problems: Like any technology, VR can face technical problems such as hardware or software failures, or Internet connectivity problems. To mitigate this risk, backup equipment will be available and appropriate training will be provided to healthcare personnel to handle VR equipment. Fast and efficient technical support will also be guaranteed to resolve any issues that may arise.

4- Technical problems: Like any technology, VR can face technical problems such as hardware or software failures, or Internet connectivity problems. To mitigate this risk, backup equipment will be available and appropriate training will be provided to healthcare personnel to handle VR equipment. Fast and efficient technical support will also be guaranteed to resolve any issues that may arise.

5- Exclusion of certain patients: Some patients may not be able to participate due to severe cognitive impairment, dizziness, certain visual impairments or other health conditions, which could potentially lead to feelings of exclusion or frustration. To mitigate this risk, communication with patients about the limitations of who can participate in the study will be clear, explaining health and safety reasons. For those patients who are unable to participate, other alternative activities or interventions will be explored.

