8. MANAGEMENT AND COMMUNICATION OF ADVERSE REACTIONS

As this study uses virtual reality in cognitive stimulation for patients with cognitive impairment and does not involve the use of medications, the management and communication of adverse drug reactions is not applicable in this context.

However, any adverse side effects associated with the use of virtual reality technology, such as dizziness, nausea or disorientation, will be carefully recorded and monitored by the research team. Healthcare professionals are trained to handle these incidents and will provide necessary care to study participants should these adverse effects occur.

The research team agrees to inform the collaborating company, Reality Telling, about any incident that occurs during the study, respecting the confidentiality of the participants. In the event of a serious adverse reaction, the research team will take necessary steps to ensure the safety of the participant and determine whether their participation in the study needs to be adjusted or discontinued.

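### The plan gives conflicting times for the primary acceptability questionnaires, and under the likelier one (once, after session 8) patients who stop early have no primary outcome

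*Combined protocol and SAP*

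**What the plan says.** **Timing of the primary questionnaires.** Section 5.4.1 names a satisfaction questionnaire and the System Usability Scale (SUS) as the main outcome, with the timing "HE will managen after the last session (the eighth". The wording is a translation artefact; the meaning is one administration after session 8. The 5.5 schedule lists these forms only at the final visit: "Completion of the VR training sessions, questionnaires on cognitive function and satisfaction and usability variables". Section 6.1 differs: "The acceptability and usability of the VR exercises will be measured through questionnaires that participants will complete after each VR session".

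**Analysis.** Section 5.7 summarises SUS scores descriptively. It names no analysis set, no session and no rule for missing forms. Its paragraph on correlation and regression refers to change in acceptability and usability.

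**Stopping early.** Section 5.3 lists as grounds for withdrawal "the appearance of health problems that may interfere with continued participation in the study, or withdrawal of consent by the participant". Section 8 says that, after a serious adverse reaction, the team will "determine whether their participation in the study needs to be adjusted or discontinued".

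**Why a patient might stop.** Section 7.1 states "Some patients may experience dizziness or disorientation with VR" and "Since VR is a relatively new technology, it can be intimidating for some patients".

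No section offers the primary questionnaires to a patient who leaves before session 8 or says how such a patient enters the primary summary. Section 5.4 lists neither sessions attended nor reason for stopping.

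**The concern.** The main hypothesis in section 3 is that patients will accept the programme well. If the only acceptability forms are completed after the last session, the answer comes only from patients who stayed to the end. Those who left because they felt dizzy, uneasy or uninterested are the patients most likely to have rated it poorly, and they would not be asked. The descriptive summary would then lean towards acceptance, and it would answer a narrower question than the one posed: how finishers rated the programme, rather than how those who started it did.

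The timing conflict matters in its own right, because the two schedules give different data. One yields a single form per completer. The other yields up to eight forms per patient, with no statement of which one is primary.

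**Working it through.** **Step 1. Set the timing statements side by side.**

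| Section | Timing it states or implies |
|---|---|
| 5.4.1 | Once, after session 8 |
| 5.5 | Final visit (session 8) only |
| 6.1 | After every session |
| 5.7 | Refers to change, so needs at least two measurements |

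Sections 5.4.1 and 5.5 are the specific ones: they define the outcome and the visit schedule. Section 6.1 is a general account of data sources. Its next sentence also departs from 5.4.1, placing the cognitive tests "before, during and after the VR training program" where 5.4.1 has only before and after. Session 8 is therefore the likelier intention, but 5.7 lends 6.1 some support and the conflict is not settled by the text.

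**Step 2. Follow an early stopper through each schedule.** Take a patient who leaves after session 3. Under 5.4.1 and 5.5 the patient has no primary form. Under 6.1 the patient has three, but 5.7 does not say which, if any, is summarised.

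**Step 3. Look for another source.** Two exist, and neither is the primary outcome. Section 8 records side effects such as dizziness and nausea. The participant feedback in 5.2 is gathered at the end of the session to improve the exercise.

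**Step 4. Size.** The plan has no figure to reproduce: the sample of 20 in 5.6 rests on pilot status and capacity, with no dropout allowance. Let *k* of 20 starters stop before session 8, let *C* be the mean item score of completers, and let *S* be the mean that stoppers would have given. Items are scored so that higher is more favourable, with one step between adjacent response options.

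- All-starter mean = [(20 − *k*)*C* + *kS*] / 20
- Completer mean minus all-starter mean = (*k*/20) × (*C* − *S*)

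Annex 7 offers five response options, so the gap *C* − *S* on an item cannot exceed 4 steps. The values of *k* and of the gap are assumptions; the documents give neither.

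| Stoppers *k* | No gap | 1-step gap | 2-step gap | 4-step gap (ceiling) |
|---|---|---|---|---|
| 1 | 0 | 0.05 | 0.10 | 0.20 |
| 2 | 0 | 0.10 | 0.20 | 0.40 |
| 4 | 0 | 0.20 | 0.40 | 0.80 |

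The last column needs every stopper and every completer to sit at opposite ends of the scale. It is a bound, not an expectation.

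**Step 5. How likely is any loss?** If each of 20 patients independently has an assumed 5%, 10% or 20% chance of stopping, the chance of at least one missing primary outcome is 1 − 0.95^20 = 64%, 1 − 0.90^20 = 88%, or 1 − 0.80^20 = 99%.

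**The case against.** **Section 6.1 may be what was meant.** A reader might infer that 6.1 is simply a stray error and that the plan is firmly completer-only. The documents do not support that much, because the reference to change in 5.7 fits repeated forms. If 6.1 governs, early stoppers already have data, and a rule to use their last form would close the gap. This stands, and the fix below allows for it.

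**Stopping may be rare.** Eight sessions at two a week take about four weeks and fall on existing appointments (5.2). Patients with high sensitivity to motion sickness or with epilepsy are excluded (5.3). Sessions are seated, supervised and introduced gradually (7.1). All of this may limit the number who stop, though the plan still foresees withdrawal.

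**It is a small descriptive pilot.** No acceptance threshold is set, so no formal decision turns on a shift of a fraction of a step. That limits the severity. Acceptability is nonetheless the study's declared primary purpose, and 7.1 ties continued use of the tool to positive results.

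**Reasons for stopping would not be wholly hidden.** A reader might infer that nothing would show why forms are missing. That goes too far: side effects are recorded under section 8, and adherence is among the aims in sections 3 and 4.2. Stops caused by discomfort could be partly traced. Stops from disinterest or unease would not be, and adherence has no defined variable in 5.4.

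**The Annex 7 item on having to stop.** A reader might infer that session-8 forms would show nobody having to stop while the true share equals the share who left. The item does not support this. It asks about interrupting a simulation because of discomfort, not about leaving the study. A completer may agree with it, and a patient who left for an unrelated illness may not.

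**Conclusion.** The concern holds in conditional form. The contradiction between 5.4.1 and 5.5 on one side and 6.1, with some support from 5.7, on the other is certain and affects the primary outcome. The completer-only summary follows if the session-8 schedule is used. The summary is biased towards acceptance only if stoppers accept VR less than completers do; the risks named in 7.1 make that plausible, but nothing in the documents establishes it.

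On moderate assumptions (a one-step gap and 1 to 4 stoppers) the shift is 0.05 to 0.20 step per item. This assumes that all 20 start and every completer returns a form. It should be fixed, because it touches the main hypothesis and the remedy is cheap. Confidence is medium, since the gap in the plan is clear and its practical effect is not.

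**What to change.** 1. **Reconcile the timing** across 5.4.1, 5.5 and 6.1, and bring the reference to change in 5.7 into line. Settle the cognitive-test timing in 6.1 in the same edit.
2. **Give early stoppers a form.** If the single session-8 measurement is kept, offer the same satisfaction questionnaire and Annex 7 at the last session attended or at exit to anyone who stops early and agrees. If the per-session forms of 6.1 are kept, name session 8 as the primary form and use the last available form for early stoppers.
3. **Define the summary set in 5.7** as all patients who start session 1. Show completers separately and state how many starters have no form. Tabulating each item by response category is enough; no total score or cut-off is needed for this.
4. **Record and report** sessions attended out of 8 and the reason for stopping, allowing for none given. This also supplies data for the adherence aim in sections 3 and 4.2.

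**Cost.** Short edits to 5.4, 5.5, 5.7 and 6.1, and an attendance record. Under the session-8 option, add one set of forms per willing early leaver (8 + 8 = 16 Annex 7 items plus the satisfaction questionnaire). Under the 6.1 option, the forms are completed at every session. The all-starter summary mixes lengths of exposure from 1 to 8 sessions, so sessions attended should be shown beside it. The headline figure may be less favourable.

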5.2 Design

This study will be prospective and non-randomized in design. Patients will be selected from among those who already attend cognitive rehabilitation sessions at the CSSC Day Hospital. There will be no control group in this pilot study, as the primary objective is to evaluate the usability and acceptability of the intervention.

Experimental group: This group will be made up of 20 patients who attend cognitive rehabilitation sessions at the CSSC Day Hospital. These patients will participate in 8 cognitive rehabilitation sessions that will incorporate the VR experiences developed for this study.

Intervention

Sessions:

The 8 sessions will be held two days a week, at the time when the included participants have an appointment for the conventional cognitive rehabilitation program at the CSSC Day Hospital.

Equipment and Technology:

We use Oculus Quest 2 glasses and their hand tracking technology, which allows for a more immersive and less complicated experience for participants, especially those with MCI.

Developed Virtual Reality Experiences:

A) Interactive Cognitive Stimulation Exercises (Declarative Memory, Executive Functions):

Developed jointly by the BSA VR and Reality Telling teams, following the researchers' guidelines, three types of sequential interactive exercises have been created:

Step 1- Make a Purchase at the Supermarket:

- Scenario: Virtual supermarket.
- Avatar: An animated avatar greets the participant and provides instructions.
- Objective: Select ingredients to make a potato omelet or gazpacho.
- Interaction: Participants use hand tracking technology to grab products and place them in a virtual cart.
- Feedback: A success or error audio is emitted based on the product selection.

Step 2- Pay for the Purchase:

- Scenario: Checkout area of the virtual supermarket.
- Avatar: An animated avatar greets the participant and provides instructions.
- Objective: Pay the exact amount for the selected products.
- Interaction: Select 3D models of bills and coins to reach the correct sum.
- Feedback: An avatar and audio provide confirmation or correction.

Step 3- Sort the Recipe Steps:

- Scenario: Virtual kitchen.
- Avatar: An animated avatar greets the participant and provides instructions.
- Objective: Sort photos of the recipe steps.
- Interaction: Drag and drop photos into a numbered panel.
- Feedback: Confirmation of the avatar.

Scenario details:

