5.6 Sample size

The sample size for this pilot study has been established at 20 patients. This decision is based on several factors:

Preliminary nature of the study: As this is a pilot study, the primary objective is to evaluate the usability and acceptability of the virtual reality intervention, rather than to demonstrate effectiveness. Pilot studies typically have smaller sample sizes than full studies.

Resources and capacity: The capacity of the El Carme Socio-Health Center in Badalona and the available resources (both in terms of staff and virtual reality equipment) also influence the sample size. Ensuring that each participant can receive appropriate care and support is

critical to accurate data collection and a positive patient experience.

Patient variability: Although the sample size is small, it is expected to reflect the diversity of the patient population in terms of severity of cognitive impairment, gender, age, etc. This diversity may provide a deeper understanding of how different types of patients may interact with virtual reality technology.

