5.7 Statistical analysis

The data collected during the study will be analyzed using statistical methods appropriate for each type of variable. All analyses will be performed using statistical software SPSS 27.0.

Acceptability and Usability: Scores obtained on the System Usability Scale (SUS) will be analyzed descriptively to provide an overall measure of the acceptability and usability of the VR intervention.

Cognitive function: Depending on the normality of the variables, statistical tests will be applied to compare scores (parametric Student's T or non-parametric Wilcoxon (in the case of failure to comply with the assumption of normality).

Demographic and clinical variables: Correlation and multiple regression analyzes will be used to examine relationships between demographic and clinical variables (e.g., age, gender, etiology, education) and changes in acceptability, usability, cognitive function, and quality of life.

The hypotheses will be evaluated at the significance level of p < 0.05 (95% confidence level). As this is a pilot study, the results will be used primarily to generate hypotheses for future research and to provide effect size estimates that may be useful for sample size calculation in future studies.

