ANNEX 3. Attention and memory test: TMT

Trail Making Test (TMT) Parts A & B

Instructions:

Both parts of the Trail Making Test consist of 25 circles distributed over a sheet of paper. In Part A, the circles are numbered 1 - 25, and the patient should draw lines to connect the numbers in ascending order. In Part B, the circles include both numbers (1 - 13) and letters (A - L); as in Part A, the patient draws lines to connect the circles in an ascending pattern, but with the added task of alternating between the numbers and letters (i.e., 1-A-2-B-3-C, etc.). The patient should be instructed to connect the circles as quickly as possible, without lifting the pen or pencil from the paper. Time the patient as he or she connects the "trail." If the patient makes an error, point it out immediately and allow the patient to correct it. Errors affect the patient's score only in that the correction of errors is included in the completion time for the task. It is unnecessary to continue the test if the patient has not completed both parts after five minutes have elapsed.

Step 1: Give the patient a copy of the Trail Making Test Part A worksheet and a pen or pencil.

Step 2: Demonstrate the test to the patient using the sample sheet (Trail Making Part A – SAMPLE).

Step 3: Time the patient as he or she follows the "trail" made by the numbers on the test. Step 4: Record the time.

Step 5: Repeat the procedure for Trail Making Test Part B.

Scoring:

Results for both TMT A and B are reported as the number of seconds required to complete the task; therefore, higher scores reveal greater impairment.

Average Deficient Rule of Thumb Trail A 29 seconds > 78 seconds Most in 90 seconds Trail B

75 seconds > 273 seconds Most in 3 minutes

Sources:

- Reitan RM. Validity of the Trail Making test as an indicator of organic brain damage. *Percept Mot Skills*. 1958;8:271-276.

Trail Making Test Part A

Patient's Name: Date:

Trail Making Test Part A – SAMPLE

Trail Making Test Part B

Patient's Name: Date:

Trail Making Test Part B – SAMPLE

Institut Català de la Salut

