ANNEX 4. Attention and memory test: SDMT

Institut Català de la Salut

ANEXO 5. Montreal Cognitive Assessment (MoCA)

ANEXO 6. Mini-Mental State Examination (MMSE)

Mini-Mental State Examination (MMSE)

Patient's code:

Date:

Instructions: Ask the questions in the order listed. Score one point for each correct response within each question or activity.

Maximum Score	Patient's Score	Questions
5		"What is the year? Season? Date? Day of the week? Month?"
5		"Where are we now: State? County? Town/city? Hospital? Floor?"
3		The examiner names three unrelated objects clearly and slowly, then asks the patient to name all three of them. The patient's response is used for scoring. The examiner repeats them until patient learns all of them, if possible. Number of trials:
5		"I would like you to count backward from 100 by sevens." (93, 86, 79, 72, 65, …) Stop after five answers. Alternative: "Spell WORLD backwards." (D-L-R-O-W)
3		"Earlier I told you the names of three things. Can you tell me what those were?"
2		Show the patient two simple objects, such as a wristwatch and a pencil, and ask the patient to name them.
1		"Repeat the phrase: 'No ifs, ands, or buts.'"
3		"Take the paper in your right hand, fold it in half, and put it on the floor." (The examiner gives the patient a piece of blank paper.)
1		"Please read this and do what it says." (Written instruction is "Close your eyes.")
1		"Make up and write a sentence about anything." (This sentence must contain a noun and a verb.)
1		"Please copy this picture." (The examiner gives the patient a blank piece of paper and asks him/her to draw the symbol below. All 10 angles must be present and two must intersect.)
30		TOTAL

1

(Adapted from Rovner & Folstein, 1987)

Source: www.medicine.uiowa.edu/igec/tools/cognitive/MMSE.pdf Provided by NHCQF, 0106-410 Instructions for administration and scoring of the MMSE

Orientation (10 points):

- Ask for the date. Then specifically ask for parts omitted (e.g., "Can you also tell me what season it is?"). One point for each correct answer.
- Ask in turn, "Can you tell me the name of this hospital (town, county, etc.)?" One point for each correct answer.

Registration (3 points):

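### The cognitive battery is repeated in one uncontrolled group with no alternate forms specified and no allowance for retest gain, so any such gain would be counted as cognitive improvement

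*Combined protocol and SAP*

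**What the plan says.** Section 5.4.1 lists Digits, TMT and SDMT for attention and memory, and MoCA and MMSE for general cognition. On timing it says "The evaluations will be carried out before starting the training program and at the end of it", the end being after session eight. The visit table in section 5.5 agrees: cognitive results are collected at the pre-study selection visit and at session 8, with nothing in between. Section 6.1 instead speaks of "standardized tests that participants will complete before, during and after the VR training program".

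Section 5.2 states that "There will be no control group in this pilot study", and section 5.6 that "The sample size for this pilot study has been established at 20 patients". Section 5.7 compares the scores by "parametric Student's T or non-parametric Wilcoxon" at p < 0.05 and offers the resulting effect sizes for sizing future studies. Section 3 hypothesises that attention and memory will improve after the sessions. Section 4.2 uses the before-after change to judge the programme's effectiveness.

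On materials, Annex 3 describes one layout for each TMT part; its first step is "Give the patient a copy of the Trail Making Test Part A worksheet and a pen or pencil". The MMSE form in Annex 6 leaves the recall items open: "The examiner names three unrelated objects clearly and slowly, then asks the patient to name all three of them". It also allows two attention tasks, serial sevens or backward spelling. The text names no second version of any test, practice run, repeated baseline or correction for retesting. Section 5.8 lists the missing control group, short duration, self-report and staff interaction as limitations, but not retest effects.

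**The concern.** People often score better the second time they take a test, because they remember items or know what the task demands. In a single group the before-after change is the sum of any VR effect, any retest gain and anything else that shifts over the interval. The tests in section 5.7 cannot separate these parts.

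The plan then uses the change in four ways: as a test of the improvement hypothesis (section 3), as a measure of effectiveness (section 4.2), as effect sizes for later trials (section 5.7), and indirectly in the undertaking in section 7.1 to keep the tool if results are positive and show significant benefit. A retest gain would push all four the same way. If it entered the effect size, a later trial planned on that figure would be too small.

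The missing control group is acknowledged as a pilot constraint. Which version of each test is given at which visit is a separate measurement choice, and it can be improved without adding patients.

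**Working it through.** The plan gives no power or sample-size calculation, so there is no figure of its own to reproduce.

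**Interval.** Eight sessions at two per week (section 5.2) is 8 / 2 = 4 weeks, which is roughly the shortest gap between testings. Selection runs from September to October 2023 (section 5.3), and data collection ends between December 2023 and January 2024 (section 11). From 1 September to 31 January is 152 days, the longest gap the calendar allows.

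**Inputs from the plan.** n = 20 (section 5.6); paired comparison at 0.05 (section 5.7). Sidedness is not stated; two-sided is assumed.

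**Inputs assumed.** True VR effect zero; retest gain g, in baseline SD units, from 0.1 to 0.3; retest correlation r of 0.7 or 0.8; equal SD at both visits; paired t-test. The documents supply neither g nor r.

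**Formulas.**

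- Standardised change: dz = g / sqrt(2(1 − r)). The denominator is sqrt(0.6) = 0.775 at r = 0.7 and sqrt(0.4) = 0.632 at r = 0.8.
- Noncentrality: dz × sqrt(20) = dz × 4.472.
- Probability of a significant result in the direction of improvement: upper tail of the noncentral t, 19 df, beyond 2.093.

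| r | g | dz | Probability |
|---|---|---|---|
| 0.7 | 0.1 | 0.129 | 7.9% |
| 0.7 | 0.2 | 0.258 | 19.4% |
| 0.7 | 0.3 | 0.387 | 37.6% |
| 0.8 | 0.1 | 0.158 | 9.9% |
| 0.8 | 0.2 | 0.316 | 26.9% |
| 0.8 | 0.3 | 0.474 | 52.1% |

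With g = 0 the figure is 2.5%. Widening r to 0.6–0.9 at g = 0.2 gives 15.6% to 47.6%. The smallest observed dz that reaches significance with 20 patients is 2.093 / 4.472 = 0.468.

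**Effect size.** Under the same model, the dz column is also the amount by which the paired effect size would be raised: at g = 0.2 and r = 0.7, by 0.258.

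These figures are for one test. Five are named, and section 5.7 states no adjustment across them.

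**The case against.** A reader might infer several stronger things that the documents do not support.

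- **That identical versions are reused.** Silence about alternate forms is not a statement that one form serves both visits. The SDMT and MoCA annex content is not shown, Digits has no annex, and the MMSE leaves the three objects to the examiner. What can be said is that no alternate forms are specified.
- **That the retest interval is four weeks.** That is the programme length. Baseline at the selection visit can make the gap longer, which could weaken any rehearsal.
- **That a third administration is planned.** Section 6.1 conflicts with sections 5.4.1 and 5.5 on this. The conflict needs settling, but it does not establish a mid-programme testing.
- **That a retest gain is shown to occur.** The documents contain no gain or retest correlation, and some influences may run the other way. If the eligibility MMSE (above 23) doubles as baseline, selection on a minimum score tends to lower the retest mean. Scores of 24 to 30 on a 30-point scale also leave little room to rise.

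It is also fair to say that cognition is secondary, that sections 5.6 and 5.8 disclaim demonstrating effectiveness, and that section 5.7 calls the results mainly hypothesis-generating. Alternate forms would not remove general familiarity with testing; that takes a concurrent comparison or, in part, a repeated baseline.

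All of this limits the wording and the size of the point. It does not answer the point itself: the change is still tested at p < 0.05 and its effect size carried forward, and retest effects are named nowhere.

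**Conclusion.** The point holds in a limited form. Followed as written, the plan would credit any retest gain to the VR programme, because one uncontrolled group repeats the battery with no alternate forms specified and no retest allowance in the analysis or the limitations.

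The size is conditional. With no VR effect, 20 patients, a two-sided paired t-test, an assumed gain of 0.1 to 0.3 SD and a retest correlation of 0.7 to 0.8, one test shows a significant improvement with probability of about 8% to 52%, against 2.5%. The range illustrates sensitivity; it does not estimate what will happen in this trial. The primary acceptability and usability outcome is untouched. The point is a worthwhile, inexpensive improvement to a secondary outcome.

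**What to change.** In section 5.4.1:

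- For each test with an equivalent alternate version in the study language, give one version before and the other after. Counterbalance the order by study code (20 / 2 = 10 patients per order) and record the version used.
- For the MMSE, use a different object list at each visit and the same attention task at both.

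Reconcile the testing times in section 6.1 with the two-point schedule in sections 5.4.1 and 5.5.

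For all tests, with or without alternate versions, name retest gain in section 5.8. In section 5.7, report the mean change with a confidence interval, described as including any retest gain and not attributed to VR. Attach the same caution to the effect sizes offered for future studies.

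The cost is second forms, where they can be obtained, and a version log. Versions may differ in difficulty. If one is harder by δ, the change shifts by −δ in one order and +δ in the other. That averages to zero with 10 patients in each order but adds slight noise to the change scores. Whether equivalent versions exist for every test cannot be judged from the documents; the reporting changes do not depend on it.
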